8.3 Post-operative assessments

8.3.1 Post-operative discharge

On discharge day, the following data will be recorded:

- Length of stay in hospital (days)
- Intraoperative complications
- Time till commencement of oral intake

8.3.2 Post-operative follow up

A patient phone call may be conducted on days 1,2,4,7,14 and 30 to remind them to fill in their VAS pain scores. A scheduled patient phone call on day 30 will collect the following data:

- Reoperation within 30 days
- Post operative complications

- Readmission to hospital within 30 days

They will be asked to return their VAS pain CRF to the study team via a pre-paid envelope provided.

8.4 Schedule of trial assessments

Assessment/ Procedure	Screening and baseline	Surgery (Day 0)	Day of discharge	Follow up					
				POD 1	POD 2	POD 4	POD 7	POD 14	POD 30
Eligibility (inclusion/ exclusion criteria)	x								
Written informed consent	x								
Registration	x								
Assignment of a unique participant identification number	x								
WHO performance score	x	x							
Randomisation		x							
Pain VAS score		x	x	x	x	x	x	x	x
Participant demographics – age, gender etc.	x								
Diagnosis and proposed surgery	x	x							
TOLR/ transoral surgical excision		x							
Surgeon's survey		x							
Return to theatre within 24 hours				x					
Length of hospital stay			x						
Readmission to hospital within 30 days									x
Return to theatre within 30 days									x
Intra operative complications			x						
Post operative complications				x	x	x	x	x	x
Time till oral intake			x	x					x

9 Adverse effects and safety reporting

9.1 Definitions

PuraBond® PROOF is a non-CTIMP study as defined by the MHRA due to PuraBond® being a class III CE marked medical device not a drug. Thus, the following definitions are applicable to this study:

Term	Definition
Adverse Event (AE)	Any untoward medical occurrence in a patient or clinical study subject, including unfavourable and unintended signs, including abnormal laboratory results, symptoms or a disease associated with treatment.
Serious Adverse Event (SAE)	Any AE that: 
• Results in death• Is life-threatening• Requires hospitalisation, or prolongation of existing inpatients' hospitalisation• Results in persistent or significant disability or incapacity• Is a congenital anomaly or birth defect.
Suspected Unexpected Serious Adverse Event (SUSAE)	Any SAE, the nature and severity of which is not consistent with the Reference Safety Information (RSI) for the trial treatments – transoral surgery or PuraBond® application to the surgical field.

Medical judgement should always be exercised in deciding whether an AE is serious in other situations. Important AEs that are not immediately life-threatening or do not result in death or hospitalisation but may jeopardise the subject or may require intervention to prevent one of the other outcomes listed in the definition above, should also be considered serious.

9.2 Reporting procedures

Any questions concerning adverse event reporting should be directed to the CI in the first instance.

9.2.1 Adverse Events (AE)

An AE has been defined above (see section 9.1). It may or may not be related to the transoral surgical procedure or PuraBond® application to the surgical field. Any AE should be recorded, this can be done on the designated CRF and in the patient electronic hospital medical records.

A list of expected complications of transoral surgery include:

- Teeth, lip, gum injury
- Cutaneous or intraoral laser injury
- Pain
- Haemorrhage
- Surgical site infection
- Velopharyngeal insufficiency
- Difficulty swallowing
- Lingual or hypoglossal nerve injury

- Pharyngocutaneous fistula

A list of expected complications of PuraBond® application include:

- Irritation/inflammation, or disruption of blood components, due to the low pH of the product.
- Thromboembolism following migration of thrombus resulting from haemostatic effect.
- Embolization of gelled product following migration into blood vessels before or after gelation.

The above listed complications can be used as the RSI when assessing the expectedness of SAEs causally to the trial treatments.

9.2.2 Serious Adverse Events (SAE)

All SAEs (see section 9.1) must be reported immediately with 24 hours of knowledge of the event apart from a hospitalisation because of expected complications of transoral surgery or PuraBond® application as defined above (see section 9.2.1) which will not require expedited reporting.

A SAE form should be completed and sent to either the CI or study co-investigators (see SAE reporting form). All SAEs should also be reported to the relevant NHS research ethics committee where in the opinion of the CI, the event was both related to the study (it resulted from the administration of any of the research procedures) and unexpected (an event that is not listed in the protocol as an expected occurrence). These should be sent within 15 days of the CI becoming aware of the event. The CI should also inform the sponsor regarding any SAE.

10 Data management

The University of Liverpool, as Sponsor, has overall responsibility for the security, maintenance, and integrity of the study. The study's CI and study co-investigators are responsible for data held locally at LUHFT and for ensuring all data provided is subject to written informed consent.

10.1 Data collection and study database

Data will be collected according to the study protocol and by approved, delegated members of the study team only. Data will be recorded on the designated CRF and then transcribed over onto a specifically designed electronic data capture system. The REDCap (Research Electronic Data Capture) database that will be used in this study is encrypted and password protected. Only approved and delegated study team members will be given access to the study's REDCap database for data insertion. Access to this database is controlled by means of user identifiers and passwords, thus an audit trail will be available. Participants will be assigned a unique study identification number on registration, and this will be used on subsequent CRFs and database reporting, thus maintaining the strictest patient confidentiality.

10.2 Training

All members of the study team will be educated on the trial protocol at a departmental meeting. This will allow members of staff the opportunity to ask questions to ensure they are confident and comfortable with all aspects of the study protocol. Furthermore, the CI and study co-investigators will confirm surgeon credentialing through prior experience with PuraBond® before any surgery is performed. Study team members that are approved to use REDCap will undergo further training on how to use this database.

10.3 Patient data

All data collected for the study will be pseudonymised using unique identification numbers. Thus, a master patient identification list will be created and held securely on the password-protected encrypted NHS servers at LUHFT, ensuring it is securely and confidentially stored on site. Direct access to patient identifiable data, including access to the master patient identification list to enable reversal of pseudonymisation, will be granted to specific individuals or authorised representatives, and regulatory authorities only on request for monitoring, audit and inspection purposes.

11 Trial management

11.1 Trial committees

11.1.1 Patient and public involvement group

Patient involvement and advice will be sought from some members of the Merseyside regional head and neck cancer patient and carer support group. This includes patients who have previously undergone head and neck surgery at the study setting. Their input on key study elements will be incorporated into the study protocol. Furthermore, their involvement in reviewing the study PIS is vital.

11.1.2 Trial oversight

The Trial Management Group (TMG) will consist of the CI, study co-investigators and representatives from LCTC. This group will be responsible for the daily running of the trial. A small independent Trial Steering Committee will be convened for this study on the basis that the surgery performed and PuraBond® intervention are already in routine clinical use and both treatment arms are considered standard of care (see appendix 2). No Independent Data Management Committee (IDMC) is being proposed for this study.

11.2 Risk assessment

Given both treatment arms are already used throughout the UK and in head and neck surgical operations at the study site of LUHFT, the risk to all the study participants is no higher than that of standard care. In fact, a case series on PuraBond® use in transoral surgery reported no significant adverse events. A higher evidence study, such as PuraBond® PROOF, is needed to prove efficacy. A trial risk assessment will be performed to identify the potential hazards associated with the trial and their likelihood of occurring.

PuraBond® is a class III CE marked medical device not a drug, it is being used within its license for this study. The following risks have been identified for PuraBond® use:

- Irritation/inflammation, or disruption of blood components, due to the low pH of the product.
- Thromboembolism following migration of thrombus resulting from haemostatic effect.
- Embolization of gelled product following migration into blood vessels before or after gelation.

It is important to stress that such side effects would be the same for participants enrolled onto the study as for those patients not enrolled in the study but are treated with PuraBond® routinely as per the operating surgeon's preference. The level of risk that a trial participant would be exposed to is the same of that they would encounter outside of the trial as its use is standard of care.

11.3 Participant withdrawal

By consenting to this trial, participants are accepting of the trial interventions, assessments and follow up data collection requirements. However, at time of informed consent, patients will be reminded that their participation is voluntary, and they retain the right to withdraw from the study without reason and without prejudicing any further treatment. The sample size calculation accounts for some participant withdrawal, so it is not anticipated that it will be necessary to replace participants who decide to withdraw.

If a participant does decide to withdraw from this study, they can do so at any time by informing the CI or any other member of the research study team by calling [name]. The contact details of the study team are recorded on the PIS. The investigator will need to clarify whether the participant wishes to withdraw from all or only particular trial components. If the latter is requested, then follow up data collection for which the participant previously consented to may continue. Should any participant wish to withdraw fully from the study, any data collected prior to withdrawal may be retained and used in trial analysis as specified by the study protocol. If following randomisation, the participant does not go on to have their surgery they should be withdrawn from the trial.

11.4 Lost to follow up

If a participant is lost to follow up, the study team will attempt to contact the participant to obtain information on their status in the first instance. Otherwise, the patient will be considered withdrawn from the study (see section 11.3).

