12.2.2 Secondary outcome measures

This will include data on:

- Post-operative analgesia usage (including drug used, dose, route and frequency)
- Post-operative complications by Clavien Dindo Classification including wound infection and bleeding rates
- Length of stay in hospital
- Readmission to hospital within 30 days post operatively
- Bleeding events including primary (24 hours post operatively) and secondary (day 1 to 30 post operatively) haemorrhage
- Return to operating room within 24 hours post operatively
- Return to operating room within 30 days post operatively
- Surgeon survey regarding ease of PuraBond® use
- Time taken to normal oral dietary intake (days)
- Any health economic benefits of PuraBond® use.

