12.4 Statistical analysis

All data will be collected using the trial CRF and will be included in the final analysis. A detailed statistical analysis plan will be developed before the analyses are conducted. The following statistical considerations will be used in this study:

Data Summaries:

Continuous data are summarised as median (inter-quartile ranges) and categorical data are summarised as frequencies of counts (percentages). All VAS pain scores will be recorded to 1 decimal point.

Missing Data:

Missing data are assumed to be rare given the study methodology and short follow up period, and analyses are thus planned on a complete case basis.

Levels of Significance:

Statistical significance will be determined using the $p < 0.05$ significance level with all results presented alongside two-sided 95% confidence intervals.

Patient groups for analysis:

All analysis will be carried out on an intention to treat basis, retaining patients irrespective of any protocol violations.

Analysis of the primary outcome:

Analysis of the primary outcome will be carried out using Analysis of Covariance (ANCOVA) techniques. Here the post-operative pain score will be analysed as the primary outcome with the pre-surgical pain score being included as an adjusting covariate. Results will be presented in terms of the difference in means (95% confidence) intervals between the two groups.

13 Informed consent, ethical and regulatory considerations

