13.1 Informed consent

Before any trial related procedures are undertaken, the patient's written informed consent must be obtained using the PuraBond® PROOF trial Informed Consent Form (ICF), which follows the PIS. Please note, only when written informed consent has been obtained from the patient and they have been registered into the trial can they be considered a trial participant.

The patient's consent to participate in the trial should be obtained by those delegated to do so such as members of the study team, research nurses or qualified members of their direct clinical team, all after a full explanation has been given. All patients must be informed of the objectives of the study, the trial design, the possible adverse events, the procedures, and personal implications of study participation. They will be informed of the strict confidentiality of their patient data, but that their medical records may be reviewed for trial purposes by authorised individuals other than their treating physician.

Patients will be provided with adequate time after being given the trial PIS to consider and discuss participation and have the opportunity to ask questions. This will be defined using patient and public involvement and engagement (PPIE) data (see PPIE survey). The study team will conduct a PPIE exercise with previous head and neck surgery patients that are part of the Merseyside & Cheshire Head & Neck Cancer Support Group. During the consent process, the investigator should determine that the patient is fully informed of the trial and their participation, in accordance with the principles of Good Clinical Practice. Patients should always be asked to sign a consent form. One copy should be given to the participant, but the original copy should be kept in the investigator site file and a further copy should be kept with the participant's hospital notes. At the time of signing the ICF, each participant must be given the names and contact details of study site staff for reporting adverse events and medical emergencies.

The right of the patient to refuse to participate in the trial without giving reasons will be respected and participants are free to withdraw from the study at any time before the last trial data collection point, that takes place at one-month postoperatively, without giving reasons and without prejudicing any further treatment.

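### Section 11.4 classes a participant who cannot be contacted as withdrawn, which leaves the plan no stated route to that patient's 30-day readmission and return-to-theatre outcomes

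*Combined protocol and SAP*

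**What the plan says.** All references are to the combined protocol and SAP.

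- **Loss to follow-up (11.4).** The team tries to contact the participant to learn their status. If that fails: "Otherwise, the patient will be considered withdrawn from the study (see section 11.3").
- **Withdrawal (11.3).** The section is written for a participant who decides to withdraw. The investigator asks whether the withdrawal is full or partial. For partial withdrawal: "If the latter is requested, then follow up data collection for which the participant previously consented to may continue". For full withdrawal: "any data collected prior to withdrawal may be retained and used in trial analysis as specified by the study protocol".
- **Source of the 30-day outcomes (8.3.2, 8.4).** "A scheduled patient phone call on day 30 will collect the following data", and the list is reoperation, complications and readmission. The schedule in 8.4 marks 30-day readmission and 30-day return to theatre at day 30 only. No record check is specified if the call fails.
- **Status of these outcomes (12.2.2).** The secondary outcomes include "Readmission to hospital within 30 days post operatively" and "Return to operating room within 30 days post operatively".
- **Missing data (12.4).** Analysis is by intention to treat, but "analyses are thus planned on a complete case basis".
- **Records (4.1, 9.2.1, 13.1).** All trial procedures, follow-up included, take place in one Trust. Adverse events can be entered in the electronic hospital record. Patients are told that "their medical records may be reviewed for trial purposes by authorised individuals other than their treating physician".

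**The concern.** Loss to follow-up and withdrawal of consent are different events. A participant who withdraws may have asked the trial to stop collecting data. One who does not answer the telephone has asked for nothing, and the consent given at entry still stands. By sending the second kind of participant through the rule for the first, 11.4 gives up outcomes that the hospital record could partly supply.

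The product is a haemostat, so bleeding, readmission and return to theatre within 30 days are the secondary outcomes a reader will look at most closely. Section 11.1.2 proposes no independent data monitoring body. With 32 patients per arm, each event counts for 1/32 = 3.1 percentage points. If patients who cannot be reached are also more likely to have had an event, leaving them out lowers the reported rates.

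**Working it through.** **Step 1. Follow the rules for a patient who cannot be reached at day 30.**

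1. Readmission and return to theatre within 30 days are due at the day-30 contact (8.3.2, 8.4). The contact fails.
2. Under 11.4 the patient is treated as withdrawn under 11.3.
3. Under 11.3, continued collection depends on a request for partial withdrawal. An unreachable patient cannot make one. The full-withdrawal branch speaks only to data already in hand. Section 11.4 does not say which branch applies.
4. Under 12.4, a patient without the outcome is not a complete case and leaves the 30-day rate.

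No instruction in this chain leads to the hospital record, although 13.1 tells patients of record review and 4.1 places the trial in one Trust.

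**Step 2. How many patients.** The plan's own total is 87 × (1 − 0.3) × 1.05 = 63.9, given as 64 (12.3). This is taken as printed; whether its adjustment factor is right is a separate matter. The attrition allowance of 5% gives 0.05 × 64 = 3.2, so about 3 patients.

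**Step 3. Expected missed events.** The documents give no event rate, so the rates here are assumptions. Let L be the number lost, p the event rate in followed patients, and r the risk in lost patients relative to followed ones.

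Missed events = L × p × r. Share of all events missed = L·p·r / [(64 − L)·p + L·p·r].

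| L | p (assumed) | r (assumed) | Missed events, both arms | Share missed | Observed rate | Full-cohort rate |
|---|---|---|---|---|---|---|
| 3 | 5% | 1 | 0.15 | 4.7% | 5.0% | 5.0% |
| 3 | 5% | 3 | 0.45 | 12.9% | 5.0% | 5.5% |
| 3 | 10% | 1 | 0.30 | 4.7% | 10.0% | 10.0% |
| 3 | 10% | 3 | 0.90 | 12.9% | 10.0% | 10.9% |

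For the last row: 61 × 0.10 = 6.1 events in followed patients and 3 × 0.30 = 0.9 in lost ones; 0.9/7.0 = 12.9% and 7.0/64 = 10.9%. With r = 1 the rate is unbiased, because numerator and denominator shrink together.

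**Step 4. An extreme case in one arm.** Suppose all 3 lost patients fall in one arm of 32, and 1 of the 29 followed has an event. The complete-case rate is 1/29 = 3.4%. The full-arm rate lies between 1/32 = 3.1% and 4/32 = 12.5%. This is a bound, not an expectation.

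**The case against.** Four stronger readings are tempting, and the documents do not support them.

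- **That safety collection is ordered to stop.** No sentence says so. Section 11.3 allows collection to go on after partial withdrawal, and its sentence on earlier data does not forbid later collection. What stands is that nothing in 11.3 or 11.4 tells the team to continue for a patient who has made no request.
- **That the lost patients are those most likely to have been readmitted, re-operated or died.** The documents hold no evidence on this. Patients may be unreachable for neutral reasons, and one readmitted to the trial's own Trust may be easier to trace. Higher risk is plausible, but it is an assumption. A bias that differs between arms needs a further assumption.
- **That a lost patient drops out of every safety outcome.** Section 8.4 also schedules complications on days 1, 2, 4, 7 and 14, and 24-hour return to theatre on day 1. Adverse events can be recorded on the CRF and in the hospital record (9.2.1), and serious events are reported once known (9.2.2). Data gathered before contact is lost may be used (11.3). These routes remain open, but they depend on the team learning of the event and are not a systematic check to day 30.
- **That one missed event would remove a large share of an arm's count.** At assumed rates of 5-10%, an arm of 32 expects 1.6 to 3.2 events, so one missed event is about 31% to 63% of that count. That figure presumes that an event has been missed. The expected loss is below one event across both arms.

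It can also be said that these are secondary outcomes in a trial sized for VAS pain, and that 12.4 promises a detailed analysis plan. Both are true. A later analysis plan can specify how missing outcomes are handled, but it does not put a collection step into 11.4.

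**Conclusion.** The point holds as a cheap improvement to data collection. Section 11.4 treats an unreachable participant as withdrawn without any decision by that participant. Because 30-day readmission and return to theatre are scheduled only at the contact that failed, the plan gives no route to them, and the patient leaves the complete-case 30-day rates.

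The expected size is small: about 0.15 to 0.9 missed events across both arms. This assumes that 3 of 64 patients are lost, that the event rate is 5-10%, and that lost patients have 1 to 3 times the risk. The rates are biased downward only if that risk is above 1, which the documents do not show. The change recovers no VAS score, so the primary outcome is not affected.

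Hospital records should not be read as a complete source either. The documents place trial procedures in one Trust, but they do not show that readmissions elsewhere or deaths in the community would appear in its record.

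**What to change.** Replace the last sentence of 11.4 with:

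> A participant who cannot be contacted is lost to follow-up, not withdrawn. Unless the participant has withdrawn consent for this, readmission, return to theatre, haemorrhage, other recorded complications and recorded vital status to day 30 are taken from the LUHFT electronic record by a delegated team member blinded to allocation where possible. The source is flagged as record only, and absence of a LUHFT entry is reported as no event recorded at LUHFT, not as confirmed event-free.

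Reserve 11.3 for participants who withdraw consent. Check that the consent form covers this use of records, as 13.1 indicates.

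The cost is a short protocol change and a record check for about 3 patients. Events at other hospitals and deaths in the community may still be missed, which is why the source has to be flagged.
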